Subjects in this study are exposed to a test contact lens. Adverse events reported before the use of the test lens should be recorded as medical history. Untoward medical events reported after the subject's exit from the study will be recorded as adverse events at the discretion of the Investigator.

All adverse events either observed by the Investigator, one of his/her medical collaborators, or reported by the subject spontaneously or in response to direct questioning, will be recorded on an adverse event form. Documentation will include a description of the adverse event, time of onset, duration of event, treatment regimen instituted, any referral to other health care providers (if needed), outcome, prognosis, and likely etiology. Habitual visual acuity will be recorded prior to the report of an adverse event (as part of the examination), upon report of the subject's report of the adverse event, and after the adverse event has resolved. All adverse events will be followed in accordance with standard of care.

The Investigator will evaluate adverse events to ensure the events are categorized correctly. Elements of categorization will include (definitions provided in following section):

- Causality - i.e. the relationship between the test lens and the adverse event (not related; doubtful; possible; probable; very likely)
- Severity - i.e. the degree of intensity of the adverse event (mild, moderate, severe)

Adverse Event (AE) Definitions

An AE is any untoward (unwanted) medical occurrence in a patient or clinical investigation subject administered a test lens, if caused by the test lens. An AE can therefore be any unfavorable or unintended sign (including an abnormal finding), symptom, or disease temporally associated with the use of the test lens if related to the test lens.

An AE includes any condition (including a pre-existing condition) that: 1) was not present prior to study treatment, but appeared or reappeared following initiation of study treatment; or 2) was present prior to study treatment but worsened during study treatment. This would include any condition resulting from concomitant illnesses, reactions to concomitant medications, or progression of disease states. Pregnancy should be documented as an adverse event and should be reported to the clinical monitor and to the Sponsor immediately upon learning of the event.

Causality Assessment

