A determination of the relationship between an adverse event and the test lens. The test lens relationship for each adverse event should be determined by the investigator using these explanations:

Not Related

An adverse event that is not related to the use of the test lens.

Doubtful

An adverse event for which an alternative explanation is more likely, e.g. concomitant treatment, concomitant disease(s), or the relationship of time suggests that a causal relationship is not likely.

Possible

An adverse event that might be due to the use of the test lens. An alternative explanation, e.g. concomitant treatment, concomitant disease(s), is inconclusive. The relationship in time is reasonable. Therefore, the causal relationship cannot be excluded.

Probable

An adverse event that might be due to the use of the test lens. The relationship in time is suggestive (e.g. confirmed by de-challenge). An alternative explanation is less likely, e.g. concomitant treatment or concomitant disease(s).

Very Likely

An adverse event that is listed as a possible adverse effect (device) and cannot be reasonably explained by an alternative explanation, e.g. concomitant treatment of concomitant disease(s). The relationship in time is very suggestive, ex: it is confirmed by de-challenge and re-challenge.

Severity Assessment

A qualitative assessment of the degree of intensity of an adverse event as determined by the investigator or reported to him/her by the subject. The assessment of severity is made irrespective of test lens relationship or seriousness of the event and should be evaluated according to the following scale:

Mild

Event is noticeable to the subject but is easily tolerated and does not interfere with the subject's daily activities. These conditions are usually asymptomatic and usually do not warrant discontinuation (temporary or permanent) of the test lens. Nonetheless, the Investigator may choose to treat the condition as a precautionary measure.

Diagnoses and conditions that are considered Mild Adverse Events include the following:

- Non-significant Infiltrative Event
- Contact Lens Papillary Conjunctivitis
- Superficial Punctate Keratitis
- Conjunctivitis: Bacterial, Viral, Allergic
- Blepharitis
- Meibomianitis
- Contact Dermatitis
- Localized Allergic Reactions
- Any corneal event not explicitly defined as serious or significant adverse event, which necessitates temporary lens discontinuation < 2 weeks

Moderate

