Event is bothersome, possible requiring additional therapy, and may interfere with the subject's daily activities. Those events that are usually symptomatic and warrant discontinuation (temporary or permanent) of the test lens (excluding Serious Adverse Events).

Diagnoses and conditions that are considered Moderate Adverse Events include the following:

- Contact Lens Induced Peripheral Ulcer (CLPU)
- Significant Infiltrative Events (SIE)
- Superior Epithelial Arcuate Lesions (SEALs)
- Any Temporary Loss of 2 Lines of BSCVA
- Other grade 3 or higher corneal findings, such as abrasions or edema
- Any corneal event which necessitates temporary lens discontinuation for \geq 2 weeks
- Non-contact-lens-related-corneal-events – ex: EKC (Epidemic Keratoconjunctivitis)

- Asymptomatic Corneal Scar

Severe

Event is intolerable, necessitates additional therapy or alteration of therapy and interferes with the subject's daily activities. A serious AE is any untoward medical occurrence that:

- Results in death
- Is life threatening
- Requires in-patient hospitalization or prolongation of existing hospitalization
- Results in persistent or significant disability/incapacity
- Has potential to cause permanent impairment of a body function
- Has potential to cause damage to a body structure and may necessitate medical or surgical intervention

Diagnoses and conditions that are considered Serious Adverse Events include:

- Microbial Keratitis (MK)
- Iritis
- Permanent decrease in best spectacle corrected visual acuity equivalent to 2 acuity lines or greater
- Central Corneal Opacity
- Central Corneal Neovascularization
- Uveitis
- Endophthalmitis
- Hypopyon
- Hyphemia
- Penetration of Bowman's Membrane
- Persistent Epithelial Defect
- Limbal cell damage leading to conjunctivalization

Upon finding an adverse event, the Principal Investigator will document the condition on the follow-up visit examination form using photos or drawings (where appropriate) that detail size, location, and depth. He/she will also complete the Adverse Event Classification (AEC) Discovery Form.

Adverse Event Follow-up

It is the Investigator's responsibility to maintain documentation of each reported adverse event. All adverse events will be followed in accordance with standard of care. Such documentation will include the following:

- Diagnosis
- A description of the adverse event or ocular complication
- Detailed drawings or photographs, when appropriate
- Time of onset
- Duration of event

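### Adverse events before test-lens use are filed as medical history with no exception for the oxygen probe, and the protocol contradicts itself on whether an adverse event must be lens-caused

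*Combined protocol and SAP*

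**What the plan says.** **Start of collection.** Safety and Adverse Events gives the rule: "Adverse events reported before the use of the test lens should be recorded as medical history". No study procedure is excepted. The following paragraph covers "All adverse events either observed by the Investigator, one of his/her medical collaborators, or reported by the subject spontaneously" or in answer to questions, so it treats observed and reported events as separate routes.

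**Definition.** Under Adverse Event (AE) Definitions, an event counts when it occurs in a "subject administered a test lens, if caused by the test lens". The next sentence repeats the limit, for signs or symptoms "temporally associated with the use of the test lens if related to the test lens". The second paragraph is broader. It takes in conditions that appear or worsen after study treatment starts and adds: "This would include any condition resulting from concomitant illnesses, reactions to concomitant medications, or progression of disease states". It also says: "Pregnancy should be documented as an adverse event".

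**Scales.** The lowest category in Causality Assessment is "An adverse event that is not related to the use of the test lens". Severity Assessment is made without regard to the lens relationship, and its Moderate list includes "Non-contact-lens-related-corneal-events". The causality scale, both in the text and on the Adverse Event Classification (AEC) Form, rates the test lens only.

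**Probe.** Background and Introduction describes the sensor being placed on the central cornea at each measurement. Clinical Study Methods plans up to five scenarios per visit in randomized order, among them an open-eye and a closed-eye condition with no lens. It has the conjunctiva checked before and between probe applications for irritation from the probe.

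**The concern.** The one study instrument applied to the cornea in every condition falls outside the start rule. Because the order is randomized, a subject may be measured once or more before wearing any test lens. The comfort assessment follows a measurement, and a negative answer to its question 2 ends the visit. A probe complaint can therefore be voiced, and the visit closed, before a test lens is worn. The rule then files it as though it preceded the study.

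After a test lens has been worn, the start rule no longer applies but the definition takes over. A probe-caused event is excluded by the first paragraph of the definition and admitted by the second.

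The protocol does not define *test lens* or *study treatment*. If the former means the Apioc designs only, events with the standard or commercial lens share the same ambiguity.

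At stake is whether non-serious probe-related events, and possibly comparator-lens events, are counted, filed as history or left out, and whether this is done alike in every subject.

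**Working it through.** **1. Texts side by side**

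| Question | Text requiring a lens cause | Text not requiring one |
|---|---|---|
| Is an event without a lens cause an adverse event? | Both sentences of the first paragraph of AE Definitions | Second paragraph of AE Definitions (concomitant illness, disease progression, pregnancy); the Not Related category; the Moderate list |
| Which non-serious events are reported within 3 working days? | Adverse Event Reporting Timeline, opening paragraph: potentially related ones | Non-Serious Adverse Events: all of them |

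If lens causation were required, the Not Related category would be empty and pregnancy could not be an adverse event. The first row is therefore a true contradiction. The second row is a smaller mismatch of scope.

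**2. Reach of the start rule.** It speaks of events *reported* before test-lens use. Whether that includes redness seen by the examiner is unclear, since the next paragraph separates observed from reported events. It does not reach findings first made at the concluding slit-lamp examination once a test lens has been worn.

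**3. How often probe contact comes first.** The protocol gives no figure to reproduce.

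Inputs: 10 subjects (Number of Subjects); up to five scenarios per visit, two of them without a lens (Clinical Study Methods); randomized order (same section).

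Assumptions: all five conditions are run at visit 1, and every order is equally likely. Let k of the n = 5 conditions count as test lenses: 3 if every study lens counts, 2 if both Apioc designs do, 1 if only one Apioc lens is used.

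- P(at least one earlier contact) = 1 − k/n
- Mean number of earlier contacts = (n − k)/(k + 1)

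| k | P(at least one) | Mean per subject | Total in 10 subjects | Share of 10 × 5 = 50 visit-1 contacts |
|---|---|---|---|---|
| 3 | 1 − 3/5 = 40% | 2/4 = 0.5 | 5 | 10% |
| 2 | 1 − 2/5 = 60% | 3/3 = 1.0 | 10 | 20% |
| 1 | 1 − 1/5 = 80% | 4/2 = 2.0 | 20 | 40% |

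Enumerating all 120 orders gives the same values. Even at k = 3, the chance that at least one of 10 subjects is affected is 1 − 0.6^10 = 99.4%.

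**4. Other schedules**

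- Two no-lens conditions and one test lens: 1 − 1/3 = 67%, mean 2/2 = 1.0.
- Two no-lens conditions and two test lenses: 1 − 2/4 = 50%, mean 2/3 = 0.67.
- Two no-lens conditions, one test lens and one other lens: 1 − 1/4 = 75%, mean 3/2 = 1.5.
- No-lens conditions always first, then three lenses in random order: 100%, mean 2 + (3 − k)/(k + 1) = 2.0, 2.33 or 3.0 for k = 3, 2 or 1.
- No Apioc lens at visit 1, with *test lens* read as Apioc: all five contacts come first.

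Repeats for poor data quality, which the measurement procedure allows, would add contacts.

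**The case against.** The best case against this is that the effect is small and the intent can be read from the rest of the section.

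- **Cause can be recorded.** Event documentation includes an entry for likely etiology, the Doubtful category covers events with a more probable alternative explanation, and the form has free text. This is true, but it helps only after an event has been accepted as an adverse event, which is the point in doubt.
- **Most text favors the broad definition.** The two conditional clauses are the outliers, and an investigator working from the forms would probably record a probe abrasion after lens wear as Not Related or Doubtful. That is fair for events after lens wear. It does not touch the start rule, which is tied explicitly to the test lens.
- **Irritation is monitored anyway.** Redness is checked between contacts, and there is a concluding slit-lamp examination. However, the redness and comfort checks are written only as reasons to end the visit; neither is linked to recording an event.
- **The comfort form does not ask about the probe.** Its first question concerns the lens and its second only willingness to continue. This stands: a negative answer is not in itself an adverse event. A complaint behind it could be.
- **The share is flattered by using visit 1 only.** With five conditions at three visits there are 10 × 5 × 3 = 150 contacts, and 5 to 20 of them is 3.3% to 13.3%. This is a fair alternative denominator. The proportion of subjects affected does not change.
- **The reporting mismatch forces no breach.** Reporting every non-serious event satisfies both sentences. This is correct, and the item is minor.

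**Conclusion.** The concern holds. The start rule, followed as written, misfiles a probe-related complaint made before the first test lens, and the definition contradicts itself, the causality scale and the severity lists.

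Under equally likely order with five conditions at visit 1, 40% to 80% of subjects have a probe contact before the first test lens, depending on what counts as one. With fewer lenses the range is 50% to 75%, and it reaches 100% if the no-lens conditions come first. These figures measure opportunity, not harm. The protocol gives no rate of probe injury, so the number of misfiled events cannot be estimated.

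The consequence is limited to how completely and consistently non-serious events are recorded. Serious events are defined without a lens qualifier, and all those in the study period must be reported. The study objectives contain no safety endpoint, and the oxygen-uptake comparison is untouched. The text should be corrected, but the flaw does not threaten the main result.

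**What to change.** 1. In Safety and Adverse Events, start collection at consent or at the first study procedure, and reserve medical history for conditions present before then. State that this applies to events the examiner observes as well as those the subject reports.
2. In Adverse Event (AE) Definitions, delete the two clauses that make lens causation or relatedness a condition of being an adverse event.
3. Define *test lens* and *study treatment*, saying whether comparator lenses and the probe are included.
4. On the AEC Form, allow attribution to the probe or procedure, or to a comparator lens, as well as to the Apioc lens.
5. Align the scope of 3-working-day reporting in the opening paragraph of Adverse Event Reporting Timeline with that under Non-Serious Adverse Events.

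The cost is protocol wording and one form field. The only downside is that a few more mild events will be recorded.

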Appendix

Comfort Assessment

1. Please make a mark on the line to tell us your answer. How much discomfort did you feel with the contact lens on your eyes?

N/A

2. Please circle your answer. Subjectively, do you feel comfortable doing another measurement today?

Yes

No

Brien Holden Vision Institute Grading Scales

**BRIEN HOLDEN®
VISION INSTITUTE**

GRADING SCALES*

1. TRACE **2. MILD** **3. MODERATE** **4. SEVERE**

[figure not shown]
BULBAR REDNESS

LIMBAL REDNESS

PALPEBRAL REDNESS

[figure not shown]

PALPEBRAL ROUGHNESS

CORNEAL STAINING - TYPE

MICROPUNCTATE **MACROPUNCTATE** **COALESCENT** **PATCH**

Adverse Event Classification (AEC) Form

Adverse Event Onset Date (MMM/DD/YYYY): _____ / _____ / _____				
Eye:	OD	OS	OU	N/A (mark N/A if AE is not related to the eyes)
AE Number	_____	Subject Number	_____	AE Number
Specify Adverse Event	
_____
 
_____
 
_____
 
_____
 
_____
			
Causality	
Not Related - An adverse event that is not related to the use of the test lens.
 
Doubtful - An adverse event for which an alternative explanation is more likely, e.g. concomitant treatment, concomitant disease(s), or the relationship of time suggests that a causal relationship is not likely.
 
Possible - An adverse event that might be due to the use of the test lens. An alternative explanation, e.g. concomitant treatment, concomitant disease(s), is inconclusive. The relationship in time is reasonable. Therefore, the causal relationship cannot be excluded.
 
Probable - An adverse event that might be due to the use of the test lens. The relationship in time is suggestive (e.g. confirmed by de-challenge). An alternative explanation is less likely, e.g. concomitant treatment or concomitant disease(s).
 
Very Likely - An adverse event that is listed as a possible adverse effect (device) and cannot be reasonably explained by an alternative explanation, e.g. concomitant treatment of concomitant disease(s). The relationship in time is very suggestive, ex: it is confirmed by de-challenge and re-challenge.
			
Severity	
Mild - Event is noticeable to the subject but is easily tolerated and does not interfere with the subject's daily activities.
 
Moderate - Event is bothersome, possibly requiring additional therapy, and may interfere with the subject's daily activities.
 
Severe - Event is intolerable, necessitates additional therapy or alteration of therapy and interferes with the subject's daily activities.
			
Treatment Implemented and Recommended Follow-up	
_____
 
_____
 
_____
			
Signature of Examiner	
_____ / _____ / _____
 
Signature (MMM/DD/YYYY)
			

Adverse Event Follow-up Form

Adverse Event Follow-up Date (MMM/DD/YYYY): _____ / _____ / _____

Eye: OD OS OU N/A (mark N/A if AE is not related to the eyes)

AE Number _____
